1. RESEARCH QUESTIONS

1.1. OVERVIEW OF RESEARCH QUESTIONS

Please state the research question(s) that the evaluation intends to answer and for each research question indicate the type: implementation or outcome.

- *Implementation Questions: Identifying whether a program has been successful in attaining desired implementation goals (e.g., reaching intended target population, enrolling intended number of participants, delivering training and services in manner intended, etc.)*
- *Outcome Questions: Identifying whether program is associated with intended outcomes for participants (e.g., do participants' knowledge, attitudes, behaviors, or awareness change?)*

No	Research Question	Implementation or Outcome?
I1	To what extent were services offered and provided as intended?	Implementation
I2	To what extent is the Fresno Fatherhood curriculum and services offered to and completed by participants?	Implementation
I3	To what extent did the CQI Team carry out the steps in the CQI Plan each program year?	Implementation
R1	Will Fresno Fatherhood program participants experience significant increases in healthy parenting attitudes/beliefs/expectations after completing the Fresno Fatherhood program?	Outcome
R2	Will Fresno Fatherhood program participants experience significant increases in healthy parenting behaviors one year after program enrollment?	Outcome
R3	Will Fresno Fatherhood program participants experience significant increases in healthy co-parenting behaviors one year after program enrollment?	Outcome
R4	Will Fresno Fatherhood program participants experience significant increases in healthy employment attitudes/beliefs/expectations after completing the Fresno Fatherhood program?	Outcome

R5	Will Fresno Fatherhood program participants experience significant increases in healthy employment behaviors one year after program enrollment?	Outcome
R6	Will Fresno Fatherhood program participants experience significant increases in healthy financial attitudes/beliefs/expectations after completing the Fresno Fatherhood program?	Outcome
R7	Will Fresno Fatherhood program participants experience significant increases in healthy financial behaviors one year after program enrollment?	Outcome

* you may add rows by hitting the tab button, or right click and select insert row below

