4. HYPOTHESES

For each specified research question, state the hypothesized result(s) and briefly describe why these results are anticipated.

Research Question	Hypothesized Result
I1	We expect that services will be offered and provided as intended.
I2	We expect that Fresno Fatherhood curriculum and services will be offered to and completed by participants.
I3	We expect that the CQI Team will carry out the steps in the CQI Plan during each program year.
R1	Fresno Fatherhood program participants will experience significant positive increases in healthy parenting attitudes/beliefs/expectations immediately following program completion.
R2	Fresno Fatherhood program participants will experience significant positive increases in healthy parenting behaviors one year after program enrollment.
R3	Fresno Fatherhood program participants will experience significant positive increases in healthy co-parenting behaviors one year after program enrollment.

R4	Fresno Fatherhood program participants will experience significant positive increases in healthy employment attitudes/beliefs/expectations immediately following program completion.
R5	Fresno Fatherhood program participants will experience significant positive increases in healthy employment behaviors one year after program enrollment.
R6	Fresno Fatherhood program participants will experience significant positive increases in healthy financial attitudes/beliefs/expectations immediately following program completion.
R7	Fresno Fatherhood program participants will experience significant positive increases in healthy financial behaviors one year after program enrollment.

* you may add rows by hitting the tab button, or right click and select insert row below

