### Defining analysis measures

For each outcome construct, we have identified the relevant measures from nFORM that are theoretically aligned with that construct. We will generate a correlation matrix between items in a given construct to ensure that theoretically related items are also empirically related in our data set. Items that are not strongly correlated with other items in a construct will be removed as necessary. Factor analysis will be used to ensure that all construct items hang together (using an alpha of 0.7 or higher as the threshold). If an alpha of 0.7 cannot be obtained, that outcome will be removed.

Once we are confident that all of the items align with a given construct, we will create a composite measure by taking an average of the scores on each non-missing item in the construct. The measure definition matrix below provides information on each proposed outcome. For composite measures, a change score will be calculated between a participant's pre-program composite score and post-program composite score. For standalone survey items, a change score will be calculated between a participant's pre-survey and post-survey responses.

For the sake of consistency and simplicity, parenting and co-parenting analyses will use a participant's youngest child as the focal child.

Measure	Sample	Variable Type	Data source(s)	Variable Name	Definition
Parenting attitudes	Has at least one child age 24 or younger, saw child within past month	Continuous (range from 1 to 5 where 1 is strongly disagree and 5 is strongly agree)	nFORM entrance, nFORM exit	Par_Att	Average of 7 survey items that relate to frequency of key parenting attitudes.

Parenting behaviors	Has at least one child age 24 or younger, saw child within past month	Continuous (range from 1 to 5 where 1 is never and 5 is every day or almost every day)	nFORM entrance, OLLE 1-year follow-up	Par_Beh	Average of 7 survey items that relate to frequency of positive interactions with participant's youngest child.
Co-parenting behaviors	Has at least one child age 24 or younger	Continuous (range from 1 to 5 where 1 is strongly disagree and 5 is strongly agree)	nFORM entrance, OLLE 1-year follow-up	Copar_Beh	Average of 11 survey items that relate to positive interactions with the mother of participant's youngest child.
Financial behaviors	Has at least one child age 24 or younger	Dichotomous (0/1)	nFORM entrance, OLLE 1-year follow-up	Fin_Beh	Binary measure of having opened a checking/savings account.

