Financial attitudes	All study participants	Continuous (range from 1 to 5 where 1 is strongly disagree and 5 is strongly agree)	nFORM entrance, nFORM exit	Fin_Att	Average of 4 survey items that relate to levels of agreement with key financial attitudes.
Employment behavior	All study participants who came into the program without a resume	Dichotomous (0/1)	nFORM entrance, OLLE 1-year follow-up	Emp_Beh	Binary measure of having a completed resume to give employers.
Employment attitudes	All study participants	Categorical (range from 1 to 5 where 1 is never and 5 is always)	nFORM entrance, nFORM exit	Emp_Att	Average of 4 survey items that relate to levels of agreement with key employment attitudes.

**Commented [A1]:** Shouldn't this be OLLE 1-year follow-up? Same for employment behavior below.

**Commented [A2R1]:** Yes!

**Commented [A3]:** Also, FYI, I updated the year for the plan updated date in the headers.

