#### **Analytic approach**

The main goal of this descriptive study is to assess pre-to-post change scores in the attitudinal outcomes listed above, and assess pre-to-one-year follow-up change scores in the behavioral outcomes listed above among program participants before and after primary workshops. We will use paired sample t-tests to assess the magnitude and significance of changes among program participants in the analytic sample for each outcome. For binary economic stability outcomes, we will descriptively report the percent of participants who opened a checking or savings account 1 year after enrollment, compared to the percent who had opened these accounts before the program. For binary employment outcomes, we will descriptively report the percent of participants who did not have a resume 1 year after enrollment, compared to the percent who did not have a resume before the program. We will adjust our p-values for multiple hypothesis testing and report the adjusted p-values in the appendix of the final report.

For the implementation analysis, program fidelity will be descriptively reported by the percentage of enrolled participants who receive: 1) any primary workshops, 2) employment supports, 3) substantive service contacts, 4) referrals. The program aims to provide all participants each of these four program components, so the percentage of participants who receive each of these will be compared to the 100% benchmark. Number of substantive service contacts per participant will also be compared to the benchmark of 8 SSCs set by OFA for FIRE grantees.

Exploratory analysis will examine how dosage varies by workshop characteristics (e.g., timing and length of sessions) and participant characteristics (e.g., age, employment status, relationship status).

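### R5 and R7 ask for significant increases, but the SAP gives their two binary outcomes only before-and-after percentages, and the R5 sample fixes its before figure at 100%

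*SAP*

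**What the plan says.** Protocol section 1.1 (R5) asks about "significant increases in healthy employment behaviors one year after program enrollment". Section 4 hypothesises for R7 that participants "will experience significant positive increases in healthy financial behaviors" at one year.

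The SAP measures each question with one 0/1 variable. For R7, Fin_Beh is a "Binary measure of having opened a checking/savings account". For R5, Emp_Beh records having a completed resume, and its sample is "All study participants who came into the program without a resume".

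Under Analytic approach, the SAP first promises "paired sample t-tests to assess the magnitude and significance of changes among program participants in the analytic sample for each outcome". It then turns to the binary outcomes. For accounts: "For binary economic stability outcomes, we will descriptively report the percent of participants who opened a checking or savings account 1 year after enrollment", compared with the percent before the program. For resumes, the planned figures are "the percent of participants who did not have a resume 1 year after enrollment, compared to the percent who did not have a resume" at entry. It then says p-values will be adjusted for multiple testing, without naming a method or listing the tests. Under Defining analysis measures it adds: "For standalone survey items, a change score will be calculated between" the pre-survey and post-survey responses, with no exception for binary items.

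**The concern.** Three things do not fit together.

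- **Question and analysis.** R5 and R7 ask about significance. Their only SAP measures receive two percentages each, with no interval and, on the natural reading, no test.
- **The R5 comparison.** In a sample chosen for having no resume at entry, the percent without one beforehand is 100% whatever the data. Nobody can get worse, so one father writing a resume counts as improvement.
- **The set of tests.** The t-test sentence and the change-score rule can be read as covering the binary items; the two sentences on binary outcomes can be read as excluding them. The adjustment therefore covers either five p-values or seven.

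The final report would have no stated basis for answering R7. Its R5 contrast could show only no change or improvement.

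**Working it through.** **Inputs.** The SAP has seven outcomes: five composites (parenting attitudes, parenting behaviors, co-parenting behaviors, financial attitudes, employment attitudes) and two binary variables. The available text gives no analytic sample size, alpha, sidedness or expected rates, so there is no plan figure to reproduce. All counts below are assumptions, judged at two-sided 0.05.

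**R7: what two percentages leave open.** Let *b* be fathers gaining an account, *c* fathers losing one, and *n* the pairs.

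- Difference: d = (b − c)/n.
- Exact McNemar p: two-sided binomial test of b out of b + c against 0.5.
- 95% CI: d ± 1.96 × √{[(b + c)/n − d²]/n}.

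Every row is a rise of 10 points, for example 50% to 60%.

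| n | gain / lose | exact p | 95% CI (points) |
|---|---|---|---|
| 150 | 20 / 5 | 0.004 | +3.7 to +16.3 |
| 150 | 30 / 15 | 0.036 | +1.4 to +18.6 |
| 150 | 40 / 25 | 0.08 | −0.4 to +20.4 |
| 100 | 20 / 10 | 0.10 | −0.6 to +20.6 |
| 300 | 60 / 30 | 0.002 | +3.9 to +16.1 |

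For the first row, d = 15/150 = 0.10 and the standard error is √{[25/150 − 0.01]/150} = 0.032. The interval is therefore 10 ± 6.3 points. The same pair of percentages supports different answers depending on *b*, *c* and *n*.

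**R5: the before figure.** If all *n* fathers in the sample lacked a resume at entry, the before percent is n/n = 100%, and *c* = 0 by definition.

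- If the t-test applies, *g* gains give t = √[g(n − 1)/(n − g)]. With g = 4: n = 50 gives t = √(4 × 49/46) = 2.06, p = 0.044; n = 150 gives t = √(4 × 149/146) = 2.02, p = 0.045. Four of 150 is 2.7%. Three gains give p = 0.083.
- Exact McNemar gives p = 2 × 0.5^g at any *n*: five gains 0.0625, six gains 0.031.

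**R5: apparent gain with no net change.** Suppose the same share *s* of all fathers switches each way, and a share *h* holds a resume at entry. The restricted sample shows a gain of s/(1 − h). With s = 5% and h = 30%, this is 0.05/0.70 = 7%. With s = 10% and h = 70%, it is 0.10/0.30 = 33%. The true net change is zero in both cases.

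**Number of tests.** Taking Bonferroni as an example, since no method is named, a raw p of 0.008 on another outcome becomes 0.008 × 5 = 0.040 or 0.008 × 7 = 0.056.

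**The case against.** The strongest defence is that the binary sentences are deliberate exceptions to a general t-test rule, and that the words about each outcome qualify the analytic sample rather than promise seven tests. That is a fair reading, and it makes the automatic-significance figures for R5 hypothetical. But it then leaves R5 and R7 with no means of judging significance. The five-or-seven doubt also persists: the only standalone items in the SAP's measure table are these two binary ones, so the change-score rule for standalone items has nothing else to apply to.

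The study is also called descriptive, protocol section 1.2 labels every outcome question Exploratory, and there is no comparison group, so no p-value would support attribution. This limits the severity. It does not remove the mismatch, because the plan itself promises significance tests and adjusted p-values. Protocol section 3 also calls behaviors the primary outcomes and describes the logic-model outcomes as confirmatory.

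The SAP's resume sentence does not repeat the sample restriction, so the percentages might be meant for all participants. In that case the measure table and the analysis text contradict each other. If the restriction does apply, the one-year figure is still useful as the complement of the proportion acquiring a resume. What fails is the comparison with the before value.

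The illustrative counts are assumed. The 40/25 case needs 65 of 150 fathers (43%) to change status in a year, and the adjustment example matters only for raw p-values between 0.05/7 = 0.0071 and 0.05/5 = 0.0100. These points bear on how often the verdict would change, not on whether the method is missing.

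**Conclusion.** The concern holds and should be corrected before the final report. R7 has no stated way to answer its own question. For an assumed 10-point rise the answer runs from p = 0.002 to p = 0.10 across 100 to 300 pairs and plausible gain/loss splits. R5's before value is 100% for any sample size once the SAP's sample definition is applied. With no net change in the full cohort, the restricted sample would still show a gain of 7% to 33%, assuming 5% to 10% switching each way and 30% to 70% holding a resume at entry. The 100% figure follows from the text alone; the other magnitudes are illustrations. Given the exploratory labels, the consequence is that the plan's own questions go unanswered, not that a confirmatory claim is invalid.

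**What to change.** **R7.** Analyse paired entrance and one-year 0/1 answers with an exact McNemar test (or another named paired binary method). Report the paired difference with its 95% CI and the counts gaining and losing an account, and include the p-value in the adjustment. Define Fin_Beh as having an account at each wave, to match items B3–B3a in protocol section 9.1, and state how the two items combine into one variable.

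**R5.** Choose one:

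- (a) Keep the no-resume sample and report only the one-year percent with a resume and its 95% CI, with no before comparison and no significance claim. At an assumed 40%, the Wilson interval is 27.6% to 53.8% for n = 50 and 32.5% to 48.0% for n = 150. The wording of R5 should then be made descriptive.
- (b) If the one-year item was asked of everyone, include all fathers with both surveys and use the same paired analysis as R7. This restores the unrestricted population in protocol sections 1.2 and 9.1.

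**Tests.** Limit the t-test sentence to the five composites, list the outcomes entering the p-value adjustment and name the method.

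Rewording both questions as descriptive would be a cheaper way to remove the mismatch over significance, but the R5 comparison would still need correcting.

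**Cost.** A few SAP sentences and one or two table cells, with no new data, and one or two more p-values in the adjusted set. Option (b) changes an analysis sample late: the SAP is dated 1/16/2025 and the protocol timeline has follow-up collection starting 4/1/2022. The change should be dated and declared.
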